Researcher Study Protocol

Official Title: The Effect of Mobile Software "Let's Move" Program Developed Based on Transtheoretical Model on Sedentary Life Behaviors of University Students

NCT ID: not yet assigned

Record Verification: 14.07.2022

SUMMARY and KEYWORDS:

Sedentary life means a physically inactive, sedentary life and is the fourth leading risk factor for global deaths. It is reported that 70% to 85% of young people between the ages of 15-24, who make up 15.6% of the population of our country, are sedentary. This rate does not meet the physical activity guidelines recommended by the World Health Organization for young people. Sedentary lifestyle causes physical, biological and mental problems, increases the prevalence of non-communicable diseases and negatively affects academic achievement. Integration of technology into human life in the health dimension; It aims to reduce the obstacles of individuals to change their unhealthy behaviors and to increase their motivation to gain healthy behaviors. The Transtheoretic Model (TTM) is an easy-to-use and proven effective model for changing the prevalence of activity. Schools are the most effective medium to reach young individuals. However, considering the density of the school population and the inadequacy of school health nurses in our country; New approach techniques and innovative strategies are needed to reduce costs and save time. Therefore, in the first stage of this twostage research, it was aimed to develop the TTM-based 'Hadi Move' mobile software program and to test the effect of the mobile software program developed in the second stage on changing the sedentary life behaviors of university students. The universe of this research consisted of 290 students studying at a foundation university in Istanbul. The sample was calculated using the G-power (3.1.9.4) program. By taking 10% more of the sample, 97 students in the experimental group and 97 students in the control group will be randomly assigned through the SPSS program. TTM-based "Let's Move" mobile software program developed for the experimental group will be applied for 12 weeks. The effectiveness of the program will be evaluated with pre-test, post-test and follow-up test, International Physical Activity Questionnaire, daily step count smart bracelet and sedentary lifestyle TTM Sedentary Life Scales (Stages of Change, Change Process Scale, Self-Efficacy and Decisional Balance Scale). At the end of the research, the effectiveness of the 'Hadi Move' mobile software program developed in this research in changing the sedentary life will be tested. In addition, it is aimed to increase the number of steps, decrease in sedentary behaviors and make an active lifestyle permanent. All initiatives developed for TTM sedentary life behavior change stages will be made into a book and the results of the experimental research will be published, contributing and providing evidence to the international literature.

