- The place and time of the research; The research was planned to be carried out between September 2021 and September 2023 with university students studying in Istanbul Beykent University Vocational School health program.
- 3. The universe of the research; The universe of the research consists of Anesthesia Program (n=57), Operating Room Services Program (n=64), Oral and Dental Health Program (n=89), Medical Imaging Techniques (n=27) and First and Emergency Aid Program at Istanbul

Beykent University Vocational School. (n=53) university freshman students studying in departments with a high number of students and meeting the criteria for inclusion in the research constituted N=290. Students who meet the inclusion criteria and volunteer to participate will be included.

4. Sample; The sample of the study was calculated with the G-power (3.1.9.4) program, means: difference between two independent means analysis. When the effect size was 0.5, type error $\alpha = 0.05$, power 1- $\beta = 0.95$, the sample size was found to be 176 (experimental group 88, control group 88). Considering the sample loss that may occur due to various reasons, it was decided to include 194 (experimental group 97, control group 97) more than 10% of the sample. The groups will be randomly assigned to the experimental control groups through the SPSS program.

5. Inclusion, Exclusion, and Exclusion Criteria

5.1.Inclusion criteria for the study;

- First year students studying in Istanbul Beykent University Vocational School health program between September 2021 and September 2023,
- ➤ 18-25 years old,
- Being in the inactive (category 1) and minimally active (category 2) categories according to the International Physical Activity Evaluation Questionnaire,
- Not included in any physical activity program,
- Do not have any physical (orthopedic, chronic diseases, etc.) and mental problems diagnosed by a doctor,
- Accepting the measurement of body weight, height, body fat and muscle ratio and calculation of BMI before starting the research, at the 12th week and at the 6th month after its completion,
- > Agreeing to use pedometer (pedometer),
- > Having an iPhone, iPod touch and android based smart phone,
- ➢ Have an active internet connection on their phone,
- Students who voluntarily agree to participate in the research will be formed.

5.2. Exclusion and Exclusion Criteria;

➢ Willingness to leave the research.

6. Data Collection Tools and Format

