Data Collection Tools; Data of the study, Socio-demographic characteristics questionnaire (Appendix 1), Transtheoretic Model (TTM) Sedentary Life Stages of Change (Appendix-2), TTM Sedentary Life Change Process Scale (Appendix 3), TTM Sedentary Life Self-Efficacy Scale (Appendix- 4), TTM Sedentar Life Decisional Balance Scale (Annex-5) and International Physical Activity Questionnaire (IPAQ) (Annex-6). The height of the students will be measured with a telescopic height meter and a scale that measures body weight, fat and muscle ratios. Step counts will be collected with the Smart Bracelet.

Data Collection Path; Students in the universe will be contacted through class representatives and informed about the right to research, and they will be invited to apply the data collection forms. Ethics committee permission, institutional permission document, voluntary consent form, socio-demographic questionnaire form, TTM Sedentary Life Scales and International Physical Activity Questionnaire will be sent to the accepted participants in the form of online forms via Google Drive.

6.1.Socio-demographic Questionnaire Form (Annex 1)

The sociodemographic characteristics diagnosis form was created by examining the relevant literature (Han et al, 2017; Tok, 2017; Baysal, 2013; Tanyeri, 2019; Ceylan, 2020). The form consists of 32 questions. In the questionnaire, there are research-oriented questions that question socio-demographic characteristics and participation in physical activity.

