Internet Usage: Internet connection is required in order to follow the users of the researcher and to receive data for research purposes. In addition, after users install the program, using the internet connection, "Let's Move" Program's message, message, etc. must be allowed to share. If it is not confirmed, the screen will appear in red.

Program Design:

"Let's Move" Program, which is a computer software program and planned as a phone application;

Content and Features of the Software		
1.screen	\checkmark Participants will set the school number as their username and will create	
	their own passwords.	
	\checkmark There will be an article explaining that the program is suitable for those who	
	are minimally active and inactive, and it will include a video about using	
	the "Lets's Move" mobile software program.	
2.screen	✓ Participants will enter their body weight, muscle and fat ratios, and height	
	into the system.	
	✓ The program will calculate the Body Mass Index and display your avatar	
	(Female/Male).	
3.screen	\checkmark The experimental group (n=97) will fill in the Sedentary Life Change Stages	
	questionnaire, the International Physical Activity Questionnaire, and the	
	Sedentary Life Scales through the Program.	
	\checkmark According to IPAQ, those who are minimally active and inactive will be	
	directed to the appropriate intervention program according to their sedentary	

		life change stage.
4.screen	✓	Students will enter the module system prepared according to five different
		stages of change [precontemplation (1), contemplation (2), preparation (3),
		action (4), maintenance (5)] of Sedentary Life.
	✓	There will be 12 different initiatives specific to each stage/module in the
		program.
	✓	There will be a total of 60 different initiatives for all phases.
	✓	Initiatives are aimed at increasing change self-efficacy and decision-
		making, prepared by using TTM change processes specific to the TTM
		change stage in which the individual is in order to accelerate behavior
		change.
	✓	Initiatives; The harms of sedentary life, the benefits of active life, how to be
		physically active, physical activity categories (inactive, minimally active
		and very active), trainings on physical activity types (light, moderate,
		vigorous) and related multiple choice questions, specific exercise for the
		change phase proposal (recipe), change plan schedule, physical
		activity/exercise videos that can be done at home, at school, in hot/cold

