Educational videos to be used in the mobile software program will be prepared in the form of animation. Opinions and suggestions of sports trainers/trainers, physiotherapists and physicians/psychiatrists were received on the contents of the "Let's Move" Program prepared by the researchers.

8. **Intervention Plan of the Research**

Students whose activity scores are inactive and minimally active according to the results of the International Physical Activity Survey (IPAQ) will be included in the study.

Program with an online satisfaction survey.

The "Let's Move" Program will be shared with the control group.

9. Independent, Dependent and Control Variables of the Study

- The independent variable of the study; Mobile Software "Let's Move" Program Developed Based on Transtheoretical Model
- Dependent variables of the study; Number of Steps per Day, Physical activity MET score categories, Transtheoretic Model sedentary life Stages of Change, SL-SES score, SL-DBS benefit perception score averages, SL-DBS harm perception score averages, Physical activity walking, moderate, severe and total MET score averages, Body Mass Index categories, fat and muscle ratio values.
- Control variables of the study; age, gender, socio-economic level, people who do sports in the family, weather conditions, environmental conditions (areas where sports can be done), previous sports status
- Limitation of the research; The inability to include students who do not have an active internet connection was accepted as a limitation of the study.

10. Analysis and evaluation of research data

The analysis of the data will be carried out on the computer with the SPSS (Statistical Package for Social Sciences) 21 package program. In the statistical analysis of the data, descriptive analyzes will be given as percentage, mean and frequency. Chi-square will be used to evaluate the homogeneity of the Experimental and Control groups, and the t test or Mann Whitney U test will be used in the analysis of the data in the experimental and control groups. One Way Anova or Kruskal Wallis analysis of variance will be applied when comparing three or more groups. Statistical significance level will be accepted as p<0.05.

11. Ethical Permissions

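### Section 10 tests the randomised arms for homogeneity and then compares outcomes unadjusted, leaving baseline activity category and gender without a role

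*Protocol*

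**What the plan says.** - **Allocation** (Summary; Materials and Methods, 4. Sample). The Summary has "97 students in the experimental group and 97 students in the control group will be randomly assigned through the SPSS program". Section 4 repeats this: "The groups will be randomly assigned to the experimental control groups through the SPSS program". Neither place names strata, blocks or minimisation.
- **Analysis** (section 10). "Chi-square will be used to evaluate the homogeneity of the Experimental and Control groups". The outcome comparison between arms is a t test or Mann-Whitney U test, with ANOVA or Kruskal-Wallis for three or more groups. For the threshold, "Statistical significance level will be accepted as p<0.05". The section does not say which variables are tested for homogeneity, and no listed outcome test carries a baseline covariate.
- **Baseline information.** Activity category is an entry criterion (section 5.1): "Being in the inactive (category 1) and minimally active (category 2) categories according to the International Physical Activity Evaluation Questionnaire". Gender is asked on the socio-demographic form (Appendix 1) and is one of seven control variables named in section 9. That section gives the control variables no use in allocation or analysis.

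**The concern.** A homogeneity test asks whether a difference between arms could be due to chance. After proper randomisation the answer is known: it is due to chance. The test cannot show that the arms are comparable, and a chance flag invites doubt about a sound trial.

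The protocol already collects two factors that plausibly predict outcome. Baseline activity category sets the room for change in MET scores and category shifts. Gender plausibly bears on fat and muscle ratios, and section 9 itself lists it as a variable to control. Testing these factors for balance and then comparing outcomes without them puts the information in the wrong place. What is at stake is some precision and the reading of the baseline table.

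**Working it through.** **The plan's own figures.** Section 4 gives 176 students (88 per arm) for effect size 0.5, alpha 0.05 and power 0.95. The exact t-test calculation gives 88 per arm one-sided (power 0.951) and 105 per arm two-sided. Adding 10%: 176 × 1.10 = 193.6, so 194, or 97 per arm. The point below uses only the 97/97 split. Sidedness is a separate matter.

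**1. Chance flags.** For k independent tests at 0.05, P(at least one flag) = 1 − 0.95^k.
- k = 3: 14%
- k = 7 (the number of control variables in section 9): 30%
- k = 10: 40%

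The value of k and independence are assumptions.

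**2. Size of chance imbalance.** If K of the 194 students have a factor, the number x in the experimental arm is hypergeometric (97 drawn from 194). The difference between arms is (2x − K)/97. With p = K/194, its standard deviation is 2·√(p(1 − p)/193). The shares are assumed, because the documents give none. The last two columns refer to the uncorrected chi-square test.

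| Share (K) | SD, points | P(difference ≥ 10 points) | Smallest difference flagged | P(flag) |
|---|---|---|---|---|
| 20% (39) | 5.8 | 7.2% | 11.3 points | 7.2% |
| 30% (58) | 6.6 | 15.8% | 14.4 points | 4.1% |
| 50% (97) | 7.2 | 15.1% | 15.5 points | 4.4% |

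By symmetry 70% (K = 136) equals 30%. The probability depends on whether K is even or odd, because 10 points means at least 10 students' difference for even K and at least 11 for odd K. Running the same formula over every K from 39 to 136 gives 7.2% to 19.6%, the maximum being at K = 96 or 98. Differences of 20 points or more have probability below 0.5% at each share in the table.

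**3. What the test misses.** At a 30% share, 15.8 − 4.1 = 11.7% of allocations have an imbalance of at least 10 points that passes as homogeneous. At 50% it is 15.1 − 4.4 = 10.7%. At 20% the two columns coincide.

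**4. Gain from adjustment.** If the baseline factors explain a share R² of the outcome variance, a model containing them has residual variance (1 − R²) times the unadjusted one. That is worth 194 × [1/(1 − R²) − 1] extra students. R² is not in the documents, so a range is assumed.
- R² = 0.02: 194 × 0.020 ≈ 4 students
- R² = 0.05: 194 × 0.053 ≈ 10
- R² = 0.10: 194 × 0.111 ≈ 22
- R² = 0.20: 194 × 0.25 ≈ 48

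**5. Extra gain from stratifying, once adjusted.** An imbalance d inflates the variance of the adjusted effect by 1/(1 − r²), where r = d/[2√(p(1 − p))]. For d = 0.10:
- p = 0.5: r = 0.100, inflation 1.010
- p = 0.3: r = 0.109, inflation 1.012
- p = 0.2: r = 0.125, inflation 1.016

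So even a 10-point imbalance costs 1.0 to 1.6% in variance, or about 2 to 3 of 194 students.

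**The case against.** The strongest reply is that nothing here is an error. Unstratified random assignment of 194 students to equal arms is valid, the unadjusted tests keep their type I error, and imbalance at 97 per arm is usually modest. Further detail could sit in an analysis plan that is not shown. The validity argument stands in full. The reply about an unseen plan stands only in part: the homogeneity tests and the unadjusted comparisons are written in section 10 itself.

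Several stronger readings are tempting but are not supported.

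- **That allocation is simple randomisation and therefore deficient.** The text is silent on the procedure. Fixed arms of 97 do not fit independent coin tosses, which would give exactly 97/97 in only about 6% of cases.
- **That stage and gender are certainly known before assignment.** Only activity category must be. The online forms go out at recruitment ("voluntary consent form, socio-demographic questionnaire form, TTM Sedentary Life Scales and International Physical Activity Questionnaire will be sent to the accepted participants"), but their order relative to assignment is not stated. Section 7 also describes a stage form completed in the app: "The experimental group (n=97) will fill in the Sedentary Life Change Stages".
- **That small stages will split badly.** A stage of 10 students would split 7–3 or worse in 33% of allocations. Section 10, however, plans no comparison of arms within a stage, and the stage sizes are unknown.
- **That a false flag is nearly certain.** Testing 20 items of Appendix 1 would give 1 − 0.95^20 = 64% under independence. But section 10 does not say these items are tested, item 20 is free text, and items 9 to 19 are related reasons given by the same student.
- **That stratifying would prevent imbalance.** It limits imbalance only on the factors chosen.

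**Conclusion.** The point holds as a low-cost improvement. The chi-square homogeneity tests should go because they cannot inform the comparison: about a 30% chance of at least one flag with seven independent tests, and at shares of 30 to 70% most imbalances of 10 points or more go unflagged. The outcome comparison should use activity category and gender, which are collected anyway. The precision gained depends on how much outcome variance they explain: about 4 to 48 students' worth for an assumed R² of 0.02 to 0.20, and less if each outcome's pre-test value is also in the model.

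A reader might infer that the missing strata undermine the trial. They do not. Once the factors are in the model, stratifying adds about 1% in variance. The figures rest on assumed shares of 20 to 70%, independent tests, the assumed R² range and the stated 97/97 split.

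**What to change.** **Section 10 (main change).** Replace the homogeneity tests with a descriptive table of baseline characteristics by arm, without p values. Compare the arms with a model that includes baseline IPAQ category and gender as factors: ANCOVA for continuous outcomes, for example, and a logistic or ordinal model with the same factors for categorical ones. This costs two sentences of protocol, collects nothing new and leaves the sample size unchanged.

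**Section 4 (optional).** State that assignment takes place after the pre-test forms are complete, stratified by IPAQ category (inactive, minimally active) and gender, with SPSS drawing half of each stratum to each arm. Keep those strata in the outcome model. This costs a few lines in the SPSS step, and assignment must wait for the forms. Even if the option is not taken, section 4 should state the allocation procedure and its timing relative to the pre-test.

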6.2. TTM Sedentary Life Scales

TTM sedentary life scales were developed by Han et al. (2015), and Turkish Validity and Reliability study was conducted by Tok (2017) with young people aged 18-24. The scale consists of 4 different parts. These; Stages of Change, Process of Change, Self-efficacy and Decisional Balance Scale (Han et al., 2015; Tok, 2017).

6.2.1. Sedentary Life Stages of Change (SL-SC) (Annex 2);

Sedentary life change stages constitute the core structure of the Transtheoretic Model. It reflects the individual's attitudes, intentions and behaviors during the change phase. Behavior change; It is a situation assessment consisting of five options and two questions: precontemplation, contemplation, preparation, action and maintenance.

- 1. Precontemplation (PC); The individual is either unaware of the problem or has little awareness of it. He has no intention of changing his problematic behavior within 6 months. Despite trying, he has failed and is reluctant. The social environment is aware of his problematic behavior and the individual feels the situation as pressure. The individual should be informed about health behavior and encouraged to think.
- 2. Contemplation (C); The individual considers the positive and negative aspects of his/her problematic behavior and is the stage where he/she thinks to change within 6 months. The individual is willing to acquire information and is ready for open

communication. However, this period consists of chronic thinking, delaying behavior and procrastination.

- **3. Preparation (P);** The individual intends to change their problematic behavior within 30 days. He has made previous attempts at behavior change, but has been unsuccessful. There are action plans such as receiving training and counseling and doing research, but they are not regular.
- **4.** Action (A); The individual changed his problematic behaviors within 6 months. It is a critical period when acquired behaviors need to be reinforced, and a return to old behaviors (relapse) may occur. At this stage, individuals need to be taught and supported skills to cope with difficulties.
- **5. Maintenance (M);** The individual has changed his unhealthy behavior 6 months ago at this stage. The individual is less affected by sedentary stimuli. Risky behaviors are less likely to recur. The individual's self-confidence has increased (Han et al., 2015).

6.2.2. Transtheoretic Model Sedentary Life Change Process Scale (SL-CPS) (Annex 3);

The process of change defines the experiences through which the individual changes behavior such as thinking, preparation, movement and maintenance. The scale consists of 40 items and two sub-dimensions, cognitive change processes and behavioral change processes. The change process scale is a 5-point Likert type. The answers to the questions are given by ticking one of the options 1: Never, 2: Rarely, 3: Sometimes, 4: Often, 5: Always (Tok, 2017).

- **6.2.2.1. Cognitive Change Processes Scale;** They are structures that evaluate the cognitive information content that the individual needs to be conscious of in order to change behavior. Individuals use cognitive change processes more in stages such as not thinking about change, thinking and preparation. The scale consists of 20 items and five sub-dimensions. These;
- Consciousness Raising; It is the increase of the individual's awareness of the problematic behavior, its negative sides, consequences and solutions. Training and conferences etc. There may be events. It consists of items 3, 15, 25, and 36 of the scale, and the Cronbach Alpha reliability coefficient of the Turkish version was found to be 0.81.
- Dramatic Relief; It refers to being warned with negative experiences related to problematic behavior. Obesity experience with sedentary life can be given as an example. It consists of items 2, 16, 21, and 31 of the scale, and the Cronbach Alpha reliability coefficient of the Turkish version is 0.81.
- > Self-Reevaluation; The individual re-evaluates healthy and unhealthy behaviors in

himself. Weighing values, using imagination, and re-evaluating healthy role models can prompt the individual to take action. It consists of items 1, 19, 26, and 38 of the scale, and the Cronbach Alpha reliability coefficient of the Turkish version is 0.80.

- Environmental Reevaluation; It is the individual's cognitive and emotional thinking about the effects of unhealthy behaviors on his/her physical and social environment. It consists of items 7, 14, 28, and 34 of the scale, and the Cronbach Alpha reliability coefficient of the Turkish version was specified as 0.73.
- Social Liberation-environmental opportunities; It is an increase in the awareness of the opportunities provided in the society against the risky behaviors of the individual. For example; Creating areas for sports in parks and gardens. It consists of items 6, 13, 22, and 32 of the scale, and the Cronbach Alpha reliability coefficient of the Turkish version is 0.74 (Tok, 2017).
- **6.2.2.2.Behavioral Change Processes Scale;** It defines the behaviors that the individual chooses during the change phase. Individuals use the processes of preparation, movement and continuation more during the behavioral change phase. The scale consists of 20 items and five sub-dimensions (Tok, 2017). These;
- Helping relationships; It includes relationships that provide trust, support and acceptance. For example, receiving counseling support, having friends and social support groups that support positive behavior. It consists of items 8, 18, 23, and 33 of the scale, and the Cronbach Alpha reliability coefficient of the Turkish version is 0.82.
- Counter Conditioning; It is the individual's choosing healthier behaviors to replace unhealthy behaviors. For example, exercising instead of playing computer. It consists of items 5, 20, 27, and 39 of the scale, and the Cronbach Alpha reliability coefficient of the Turkish version was specified as 0.85.
- Reinforcement management; It refers to self-reward as the individual changes unhealthy behaviors. It consists of items 10, 17, 29, and 40 of the scale, and the Cronbach Alpha reliability coefficient of the Turkish version was specified as 0.81.
- Stimulus Control; The individual controls the stimuli and replaces it with a healthy behavior in order to reduce the risk of relapse of the problematic behavior. For example, removing objects that support immobile behavior. It consists of items 9, 12, 24, 37 of the scale and the Cronbach Alpha reliability coefficient of the Turkish version was specified as 0.86.
- Self-Liberation; It is the individual's revealing his belief in change and adapting to change. For example, making decisions for sedentary behavior and making a promise

to himself. It consists of items 4, 11, 30, and 35 of the scale, and the Cronbach Alpha reliability coefficient of the Turkish version was stated as 0.74 (Tok, 2017).

6.2.3. Transtheoretic Model Sedentary Life Self-Efficacy Scale (SL-SES) (Appendix 4);

Self-efficacy Scale; It is an individual's belief about himself/herself that he/she can perform a certain behavior successfully, reflecting self-confidence (Han et al., 2015; Tok, 2017). The scale consists of 6 items that include self-confidence in quitting sedentary behavior. It is a five-point Likert type. It ranges from 1: Not at all trusting to 5: Very confident. The Cronbach Alpha reliability coefficient of the Turkish form of the scale was stated as 0.75 (Tok, 2017).

